## INTRODUCTION AND OBJECTIVES

### Chronic Kidney Disease and End Stage Renal Disease in Sickle Cell Disease

In adults with sickle cell disease (SCD), ~ 40% of patients have chronic kidney disease which may be associated with hypertension and albuminuria.[1] In this SCD patient population, 12% of patients progress to renal failure and 15-30% of deaths in SCD are related to kidney disease.[2,3] The treatment for a patient that has renal failure is dialysis, often as a bridge to renal transplantation. Dialysis records suggest that 0.1-0.5% of those patients initiated on dialysis for end stage renal disease (ESRD) have SCD and these patients were nearly 7 years younger than the average dialysis at the time of initiation.[4-6] The one year mortality rate for dialysis patients with SCD may be three times higher than patients with ESRD but without SCD and the mean survival time after initiating dialysis is only 4 years.[6,7] Renal transplantation is a viable option for sickle cell patients on dialysis and may improve survival.[4,5,8] However, this patient population is less likely to be offered or receive renal transplantation which may be due in part to lower survival of grafts or patients with SCD as compared to other diseases with ESRD. [8,9] The known progression to and poor survival of SCD patients with chronic kidney disease mandates early identification of patients at risk and therapies that may prevent progression.

### Sickle Cell Disease and Potential Biomarkers of Chronic Kidney Disease

Toddlers with SCD may initially develop hyperfiltration which progressively declines during adolescence and young adulthood and indicates progression to chronic kidney disease.[10,11] A cross-sectional study of adolescent SCD patients identified in-clinic systolic BP as a risk for worsening glomerular filtration rate.[12] Pediatric patients with sickle cell disease also develop microalbuminuria (microalbumin/creatinine >30mcg/mg) and proteinuria (>300mcg/mg) which may proceed kidney disease. Several studies have evaluated the presence of albuminuria pediatric sickle cell disease. (Table)

Author	Sample size	Prevalence	Correlations
McKie[13]	191	37/191 (19.4%)	Lower Hb, Age
McBurney[14]	142	Overall: 19% 7-14yrs: 18/75 (24%) 15+: 9/31 (29%)	Lower Hb, Age
Gurkan[15]	40 (33 HbSS)	MiA- 6/40 (15%) MA- 2/40 (5%) No MiA <12yrs	LDH and MiA (not correlated with HbSS alone)
Becton[16]	90	14/90 (16%)	Lower Hb, Increasing BP
McPherson[17]	261	60/261 (23%)	Lower Hb, Age
Egberue[18]	69	14/69 (20.3%) >9yrs: 23%	Age
Alvarez[19]	165 (SS and SC)	46/165 (28%) 40 HbSS. 8/46 had MA	MA vs. MiA: Lower Hb, Higher Retic, Lower GFR

Dharnidharka[20]	102	MiA (>20mg/g Cr) Overall: 26.5% 10-18yrs:46%	Age
[name][21]	144	32/144 (22%)	Low Hb
Mawanda[22]	305	86/305 (28.2%)	Low Hb, Age, more transfusions
Aygun[12]	85	15.9%	Blood Pressure, Low WBC and ANC

The novel biomarkers Kim-1 and NAG are higher in SCD patients with albuminuria.

[23,24] Cystatin C has been negatively correlated with hemoglobin and positively correlated with age, B2M and NAG.[25]

### **Abnormal Ambulatory Blood Pressure in Pediatrics is a Risk Factor for Chronic Kidney Disease:**

Hypertension, based on in-clinic BP, in SCD patients has been associated with albuminuria and hyperfiltration.[12,16,18,26-28] Additional SCD studies have associated in-clinic hypertension as a risk factor chronic kidney disease and renal failure.[9,29,30] In non-SCD pediatric populations, 24 hour ambulatory blood pressure is more accurate than clinic BP in defining secondary hypertension and abnormal 24 hr ABPM has been strongly linked to progressive renal disease.[31-35] In the large pediatric study Chronic Kidney Disease in Children (CKiD), an association was identified between abnormal ABPM and progression of proteinuria and renal function decline.[36] Despite the recent emphasis on utilizing 24 hr ABPM in clinical trials for other diseases, in SCD, the roles of hypertension defined by ABPM as a risk factor for kidney injury or intensive antihypertensive therapy to prevent the devastating complications of CKD has not been explored.

### **Selection of Angiotensin II Antagonist Therapy to Correct Abnormal Ambulatory Blood Pressure.**

Despite the high prevalence of hypertension in SCD and increased morbidity and mortality from cardiovascular disease, there are currently no randomized clinical trials in SCD to demonstrate 1) the appropriate selection of an antihypertensive medication, or 2) dosing of that medication in the pediatric setting. Angiotensin Converting Enzyme Inhibitors and Angiotensin II Antagonists both may reduce proteinuria and abnormal blood pressure in SCD patients. The rationale for selecting losartan in this feasibility trial is that unlike ACE Inhibitors, Angiotensin II Antagonists do not accumulate bradykinin which may contribute to nocturnal hypertension; losartan, unlike other Angiotensin II Antagonists, has uricosuric effect which may be important as uric acid may be associated with abnormal circadian BP and uricosuric medications may lower blood pressure (Table 4).[37-41] Of great interest, an ambulatory blood pressure clinical trial comparing an Angiotensin II Antagonist (Losartan) to an ACE Inhibitor (quinapril) demonstrated that losartan preferentially decreased nocturnal hypertension.[42] The findings of a reduction in nocturnal hypertension by Angiotensin II Antagonists was replicated in additional studies and independent of time the drug was administered. [43,44]

### **Rationale for Evaluating Safety of Using an Intensive BP Treatment Strategy**

Current standard of care in our institution is to place pediatric patients on an antihypertensive medication with a goal of reducing BP to <95th percentile based on NHLBI BP Tables for Children and Adolescent. A recent meta-analysis of 11 trials identified intensive blood pressure therapy (BP<50th or 75th percentile) as compared to standard therapy reduced adverse outcomes, most effectively in patients with concomitant proteinuria. [45] Pediatric non-SCD trials using intensive anti-hypertensive therapy guided by 24 hr ABPM resulted in decrease progression to CKD.[46,47] In a large non-SCD pediatric randomized trial of intensive vs. standard therapy for control of 24 hours blood pressure with an ACE Inhibitor, intensive BP control improved renal outcomes and the greatest impact was seen in patients with glomerulopathies.[46] As most SCD patients without renal disease have low BP relative to the black population, a target of 95 percentile BP may be physiologically hypertensive in SCD and intensive BP may be more appropriate. As no prospective anti-hypertensive trials focused on adolescent patients with SCD, it is vital to first conduct a feasibility trial to determine the safety and tolerability of standard and intensive dosing strategies

## 1.1 AIMS OF THE TRIAL

### 1.1.a Primary Objectives

To identify participants at risk for developing progressive kidney disease and to target therapeutic approaches that prevents progressive kidney disease. The primary endpoint is to conduct a randomized feasibility trial of losartan among participants with abnormal ambulatory blood pressure. We expect that 30% of participants in a pediatric hypertension cohort (n=60) will have abnormal ambulatory blood pressure and abnormal clinic blood pressure. Of these sixty participants, we estimate that 40 participants will accept enrollment in the feasibility trial.

### 1.1.b Secondary Objectives

Objective 1: To determine the acceptability of enrollment and retention in a randomized feasibility trial of losartan

Objective 2: To determine the safety of losartan at two different dosing strategies

Objective 3: To complete the necessary preparations for a definitive phase III trial including preparing a manual of operations, case report forms, and sample size calculations

## 2.0 STUDY OVERVIEW AND DESIGN

### 2.1 Study Overview.

## 2.1.a Cohort Study (X130312027) already approved cohort study being conducted)

A five year prospective cohort study will be conducted among participants with HbSS or SB0 thalassemia ages 5-22 years of age. The study will evaluate standard of care labs and medical history (including type of sickle cell therapy) to determine the incidence of hypertension and markers of progressive kidney injury. Annually, participants will undergo research evaluations using 24 hour ambulatory blood pressure monitoring and analysis of urine samples for biomarkers of kidney injury. Participants with abnormal nocturnal blood pressure dipping will be eligible for this feasibility trial.

## 2.2 Randomized Feasibility Trial-

A randomized feasibility trial of losartan for the correction of abnormal nocturnal blood pressure dipping in adolescent patients with HbSS or SB0 thalassemia 11-22 years of age who have documented hypertensive blood pressure in clinic will be conducted. Participants will be randomized to losartan at doses to maintain clinic BP either <95th percentile (standard dosing strategy) or <75th percentile (intensive dosing strategy). The study will be analyzed using intention to treat for outcomes which will begin immediately after randomization to losartan. Participants will be followed monthly as standard of care with additional research procedures of performing ambulatory blood pressure monitoring at baseline, 3 months, and 6 months and urine/blood biomarkers of kidney injury at baseline, 3 months and 6 months. We propose to identify 60 eligible participants of which 40 will participate in the randomized feasibility trial. The parents/legal guardians of these children will have a one hour educational session on hypertension and kidney disease in sickle cell disease. The parents/legal guardians will be offered the opportunity to discuss hypertension and kidney disease with a Pediatric Nephrologist prior to participation in the trial.

### 2.2.a. Eligibility for the Feasibility Trial

#### Inclusion Criteria for Pediatric Cohort (Separate IRB approved study-X130312027))

1. Participant must have sickle cell anemia (hemoglobin SS) or sickle  $\beta^0$ -thalassemia (hemoglobin S $\beta^0$ ) as confirmed at the local institution by hemoglobin analysis.
2. Participant must be 5 to 22 years of age (i.e., must not have attained their 23rd birthday).
3. Informed consent in accordance with the institutional policies (institutional IRB approval) and Federal guidelines (approved by the United States Department of Health and Human Services) must be signed by the participant's legally authorized guardian acknowledging written consent to join the study.

## 2.2.b. Inclusion Criteria for Feasibility Trial Screening

1. Enrolled in Pediatric Cohort Study
2. History of abnormal clinic blood pressure (3 abnormal blood pressure readings (systolic or diastolic) in last 4 visits) as defined by NHLBI Blood Pressure Tables for age and height.
3. History of 1) abnormal nocturnal blood pressure dipping as defined by <10% dip (daytime-nighttime systolic or diastolic blood pressure/daytime blood pressure x 100) or 2) abnormal nocturnal load defined by >25% sleep BP >95th percentile.
4. Informed consent in accordance with the institutional policies (institutional IRB approval) and Federal guidelines (approved by the United States Department of Health and Human Services) must be signed by the participant's legally authorized guardian acknowledging written consent to join the study

## 2.2.c. Exclusion Criteria for Feasibility Trial Screening

1. Participant with history of angioedema to prior ARB or ACE inhibitor
2. Participants with moderate to severe renal impairment (GFR <60mL/min/1.73m^2)
3. Co-administration of another hypertensive medication
4. History of known bilateral renal artery stenosis, unilateral renal artery stenosis to a solitary kidney
5. Hyperkalemia at time of screening (K>6 mmol/L- non-hemolyzed sample)
6. Pregnancy
7. Current use of lithium, digitalis, warfarin

## 2.2.d. Inclusion Criteria for Feasibility Trial Randomization

1. Repeat ABPM demonstrating abnormal blood pressure dipping (systolic or diastolic dipping <10%) or abnormal nocturnal load
2. Complete a Survey of Barriers and Facilitators to Enrollment in a Pediatric SCD Hypertension Trial

## 2.3 BASELINE EVALUATION AND FOLLOW-UP

### 2.3.a Baseline Evaluations

1. Screening
  - a. Eligible participants will undergo repeat 24 hour ABPM to confirm abnormal nocturnal dipping prior to randomization.
  - b. Participants, and if participants is a minor, parents/guardians, with abnormal 24 hour ABPM will be educated about hypertension, kidney disease in SCD. Participants will also be offered consult with Pediatric Nephrologist prior to randomization.
2. Randomization
  - a. Participants will have overnight urine collected for biomarker analysis. Participants can be consented to allow additional urine to be stored for future urine studies of kidney injury.

- b. Participants will have standard of care labs obtained including CBC with diff, CMP with LDH and uric acid, urine for microalbumin/creatinine ratio, Cystatin c
- c. Participants can be consented to Buccal Cell collection

#### 2.3.b Follow-up

1. Monthly evaluations (6 months total from randomization)
  - a. Participants will have monthly clinic visits
  - b. Obtain vital signs
  - c. Obtain standard of care labs: including CBC, CMP
  - d. Complete assessment of potential side effects of losartan
  - e. Complete assessment of adherence
2. Three months from randomization
  - a. Obtain overnight urine specimens for urine biomarkers including standard evaluation of microalbumin/creatinine ratio and experimental evaluation of biomarkers
  - b. Obtain cystatin C
  - c. Buccal Cell Collection
  - d. Repeat 24 hour ABPM
3. Six months from randomization
  - a. Obtain overnight urine specimens for urine biomarkers including standard evaluation of microalbumin/creatinine ratio and experimental evaluation of biomarkers
  - b. Obtain cystatin C
  - c. Buccal Cell collection
  - d. Repeat 24 hour ABPM

Table XX: Baseline and monthly evaluations

Test	Entry	1 mo	2 mo	3 mo	4 mo	5 mo	6 mo
Vital Signs, Hx and PE	X	X	X	X	X	X	X
CBC with diff	X	X	X	X	X	X	X
CMP	X	X	X	X	X	X	X
Adherence Measures		X	X	X	X	X	X
Ferritin	X			X			X
Cystatin C	X			X			X
Uric Acid	X			X			X
Urine Microalbumin/Creatinine	X			X			X
Overnight Urine Collection	X			X			X
24 hr ABPM	X			X			X
Urine and blood biomarkers	X			X			X
Pregnancy Test	X	X	X	X	X	X	X
Enrollment Survey	X						
Buccal Cell collection	X			X			X

### 3. UNDERSTANDING ENROLLMENT

All participants approached to participate in the feasibility trial have consented to the cohort study, but will be asked to complete a survey to identify barriers/facilitators to enrollment in a drug trial. Quantitative surveys questions will include Likert questions to determine barriers/facilitators to participation in this trial using two direction intensity scale (strongly agree, agree, disagree, and strongly disagree. The questionnaire will be piloted among adolescent SCD patients not eligible for the feasibility trial.

#### 4. BLOOD PRESSURE MONITORING

##### 4.1. CLINIC BLOOD PRESSURE MONITORING

Participants will have standard of care blood pressure monitoring in clinic.

Participants will have blood pressure obtained in a sitting position. Blood pressure cuffs will be selected by study member or clinic nurse and applied to the participant's non-dominant arm. The cuff bladder should cover at least two thirds of the upper arm and the bladder should encircle 80% to 100% of the circumference of the arm. Blood pressure should be measured twice in a controlled environment after 3-5 minutes of sitting.

##### 4.2. AMBULATORY BLOOD PRESSURE MONITORING

SpaceLabs 90217 monitors will be used to perform 24 hour ABPM. Participants and parents/guardians will be educated on how to operate the monitor including how to stop a reading if there is excessive discomfort, what to expect when a reading is obtained, and need to keep the arm still during BP readings. Participants will be educated that BP will be recorded every 20 minutes during the day and every 30 minutes from 10PM to 6 AM. If the monitor is removed, the device should be removed immediately after a recording and reapplied as soon as possible.

Participants should immediately contact the study team if apparent allergic reaction or extreme uncomfortable pressure. Finally, participants will be educated to keep a log book of activity during the day including activities that may influence BP. At minimum, the log should record sleep and wake times.

Blood pressure cuffs will be selected by study member and applied to the participant's non-dominant arm. The cuff bladder should cover at least two thirds of the upper arm and the bladder should encircle 80% to 100% of the circumference of the arm. The study member will allow the ABPM to inflate two times prior to leaving the clinic. Participants will receive a pre-addressed stamped FedEx box to return the diary and monitor to study team. Participants who do not complete ABPM will participate in an interview to determine the barriers to completing the ABPM and facilitators that would enhance adherence.

##### 4.3. ABPM INTERPRETATION

To be considered an acceptable procedure, the following readings must be recorded: 1) A minimum of 1 reading per hour including during sleep and 2) total of 40 readings during the period.

Values outside the following range will be discarded

- 1) SBP 60-220 mm Hg

- 2) DBP 35-120 mm Hg
- 3) Heart rate: 40-180 BPM
- 4) Pulse pressure 40-120 mm Hg

The following calculations will be recorded

- 1) Mean Ambulatory SBP and DBP for the entire 24 hour period, awake period, and sleep period
- 2) Dipping will be calculated as ((Mean Awake BP- Mean Sleep BP)/Mean Awake BP) x 100. Normal Dipping will be defined as >10% dipping. Reverse Dipping will be defined as mean sleep BP that is higher than mean Awake BP.
- 3) BP Load is the percentage of systolic and diastolic BP readings above the 95th percentile for the 24 hour, awake, and sleep periods as defined by the 2014 Statement from the American Heart Association- Update: Ambulatory Blood Pressure Monitoring in Children and Adolescents.
- 4) BP index will be calculated as the mean BP/normative data for 95th BP for the 24 hour, awake, and sleep periods.

## 5.1. URINE BIOMARKERS

Urine will be collected by the patient on any urine overnight and first urine in the morning into a sterile container provided by the study coordinator. Urine will be collected at 0, 3, and 6 months. The urine will be centrifuged and aliquoted into 10 microcontainers within one hour. Five microcontainers will be sent immediately to the UAB lab of [name] and [name]. Five microcontainers will be stored at -80 degrees Celsius at the Children's of Alabama Lab. Two of the frozen microcontainers from each participant will be sent to the UAB-UCSD O'Brien Center for Acute Kidney Injury Research, Bioanalytical Core at 3-6 month by Fed Ex Overnight shipping on dry ice to UCSD on Mon or Tues (once every 3 months). [name] at UCSD will analyze urine for Kidney Injury Marker-1 (KIM-1), Neutrophil gelatinase-associated lipocalin (NGAL), and Beta-2-microglobulin. One urine sample microcontainer tube per patient will be sent to [name] lab at UAB to be analyzed for cystatin-C, urine albumin/creatinine.

## 5.2. ADDRESSING NOVEL BIOMARKERS

Participants can consent to use of urine for future evaluations of kidney disease or hypertension. Two remaining microcontainers will be kept in a research freezer. During the course of the study, the principal investigator may be able to analyze the urine samples for novel biomarkers of hypertension or kidney injury.

## 5.3 BLOOD BIOMARKERS

Uric acid will be processed and analyzed by Children's of Alabama laboratory. 10mL of whole blood will be collected in EDTA tubes and sent to the UAB laboratory of Drs. [name] for analysis to include: thiobarbituric acid reactive substances, endothelin, aldosterone, BNP, and renin.

## 5.4. BUCCAL CELL SWABS

Participants will have buccal cell swab testing performed at three times during the study (entry, 3 mo, and 6mo). The goal of the buccal swab testing is to determine if abnormal nocturnal blood pressure in sickle cell disease is related to abnormal circadian rhythms. In animal models, an abnormal circadian rhythm is associated with hypertension. The swabs will be collected at multiple time points (6AM, 10AM, 6PM, 10PM) to determine the circadian rhythms in this patient population.

Participants will be given 3 bags: one with buccal swabs, one with labeled tubes, and an empty bag to place the tubes containing the swab tips after each collection. Holding the handle end of the swab, participants will scrape the swab collection tip firmly against the inside of the cheek 6 times (about 10 seconds). After taking the sample, the participant will eject the tip by pushing down the plunger at the end of the handle into the tube labelled for that time. Ensure the lid on the tube is tight. Place the tube into a bag and refrigerate the bag.

## 6. LOSARTAN DOSING AND MONITORING

Prior to randomization, participants will need to have 1) three documented blood pressure recordings (in last 4 visits) documenting a systolic or diastolic blood pressure that is >95th percentile for age, gender, and height as defined by NHBLI BP tables and 2) two 24 hour ABPM recordings documenting abnormal nocturnal blood pressure dipping.

6.1. Initial Dose: All participants will be initiated on 25 mg of losartan at their initial monthly visit.

6.2. Randomization scheme.

This trial will use block randomization with 6 participants per block. The blocks will be put in sealed envelopes and seven blocks out of 10 possible blocks will be selected by the pharmacist. Participants assigned A will receive intensive dosing of losartan (titrate

to keep BP <75th percentile) and B will receive standard dosing of losartan (titrate to keep BP <95th percentile).

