### 6.3. Losartan dosing

Participants will have their dose increased by the study team based on blood pressure response at monthly clinic visits to a max of 1.4mg/kg/day or 100mg/day. Dosing will be rounded to the closest 25 mg tablet. The study coordinator and PI will review the mean BP obtained by aneroid technique during the clinic visit and compared to either the 75th or 95th percentile normative data for systolic and diastolic BP by age, height, and gender. A dose can be increased for either a systolic or diastolic BP that is greater than the randomized target BP goal). Participants that miss a dose should not take an extra dose, rather the participant should resume their usual schedule. Losartan should be stored at room temperature, kept in a tightly closed container, and protected from light.

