## 9. SAMPLE SIZE AND STATISTICAL ANALYSIS

### 9.1 Sample Size

An endpoint for this feasibility trial is to determine the effect size needed to appropriately power a definitive trial of losartan to correct nocturnal dipping, rather than efficacy of losartan. Data will be collected to understand the acceptance rate, rate of recruitment, and the drop-out rate. In preliminary fashion this feasibility trial will identify the difference in nocturnal BP improvement between the two treatment arms, and within group standard deviation of BP. The feasibility trial will evaluate the change in nocturnal dipping % from baseline in all participants and among participants receiving two different dosing strategies (intensive losartan therapy (BP <75th percentile) as compared to standard dosing (BP <95th percentile)). Sample size analysis for repeated measures and adjustments to sample size to compensate for non-adherence will occur.

The feasibility trial will enroll 40 participants with hypertension (clinic and ABPM). It is expected that 30% of the 200 cohort participants will meet eligibility criteria. Of these 60 cohort participants, we expect that 40 participants will enroll in the feasibility trial. We expect a dropout rate of <10% to ensure that the feasibility trial has > 30 participants, an accepted participant size for feasibility trials.

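### A single published block size of 6, with envelopes described as holding blocks and a team that knows the arms, makes about 23% of the 40 assignments certain before entry (assuming 1:1)

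*Combined protocol and SAP*

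**What the plan says.** Section 6.2 is the whole of the randomisation text. It states "This trial will use block randomization with 6 participants per block", then "The blocks will be put in sealed envelopes", and adds that "seven blocks out of 10 possible blocks will be selected by the pharmacist". Letter A denotes the intensive target (below the 75th percentile) and letter B the standard target (below the 95th).

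The section does not give the allocation ratio, how the blocks were generated, how the seven are drawn, whether an envelope holds one assignment or six, or who opens an envelope and when.

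Masking is not mentioned. Section 6.3 does say "The study coordinator and PI will review the mean BP obtained by aneroid technique during the clinic visit" and compare it with the 75th or 95th percentile, and then "A dose can be increased for either a systolic or diastolic BP that is greater than the randomized target BP goal". Both roles therefore need to know the arm. Section 6.1 starts everyone on the same dose, so the arm need not be known until the first titration, but no delay in revealing it is planned.

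Section 9.1 plans 40 participants. Section 9.2 compares the two strategies by Student's t-test, and the Data Safety and Monitoring Board section has the board look for an excess of serious events in either group.

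**The concern.** Blocked randomisation protects against foreknowledge only if the people who decide on entry cannot work out where they are in a block. Here the block size is in the protocol and past assignments become visible through titration. Once three participants in a block have gone to one arm, the remaining places are settled.

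Before randomisation, study staff seek consent, give the education session, offer the nephrology consultation and arrange the repeat ABPM (Sections 2.2.d, 2.3.a and 10). Each step gives some control over whether, and above all when, a participant enters. With about 20 per arm, a few entries brought forward or held back in the light of a foreseen arm could shift the baseline mix. The planned t-test has no covariate adjustment to absorb that, and its results are meant to inform the size of the definitive trial.

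The envelope wording adds a second route. Read literally, the sealed unit is the block, so opening one could disclose several future assignments.

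**Working it through.** **Inputs.** Block size 6 and seven blocks out of ten (Section 6.2); 40 participants (Section 9.1); two arms (Section 6.2). *Assumptions:* 1:1 allocation, so three A and three B per block, and an observer who knows the block size and every earlier assignment.

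**The plan's own figure.** 40/6 = 6.67, rounded up to 7 blocks; 7 × 6 = 42 places for 40 participants. Seven blocks is consistent with the sample size.

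**Certain assignments.** A balanced block of 6 has C(6,3) = 20 orders. An assignment is certain once one arm has used its three places.

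| Position | 1 | 2 | 3 | 4 | 5 | 6 |
|---|---|---|---|---|---|---|
| Probability certain | 0 | 0 | 0 | 0.10 | 0.40 | 1.00 |

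- Position 4 is certain if the first three match: 2/20 = 0.10.
- Position 5 is certain if the first four split 3:1: 2 × C(3,3) × C(3,1)/C(6,4) = 6/15 = 0.40.
- Position 6 is always certain.

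The sum is 1.5 of 6, or 25% (closed form 2m/(m+1) with m = 3: 6/4 = 1.5). With 40 enrolled there are six full blocks plus four places: 6 × 1.5 + 0.10 = 9.1, and 9.1/40 = 22.75%.

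**Best-guess success.** Guessing the arm with fewer so far, and tossing a coin when level, is right with probability 0.5, 0.6, 0.6, 0.7, 0.7 and 1.0 at positions 1 to 6. That is 4.1 of 6 (68.3%) in a full block. With 40 enrolled, (6 × 4.1 + 2.4)/40 = 27/40 = 67.5%, against 50% by chance.

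**If one envelope shows a whole block to the enrolling team.** Only the first place in each block is unknown: 5/6 = 83% known in advance, or 40 − 7 = 33 of 40.

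**Varied block sizes.** Simulation with 40 enrolled, 1:1, sizes equally likely, and an observer who knows which sizes are possible but not the current one:

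| Block sizes | Certain | Best guess |
|---|---|---|
| 6 only | about 22.8% | 67.5% |
| 4, 6 and 8 at random | about 2.4% | 67.6% |

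Varying the size removes nearly all the certainty and leaves best-guess success unchanged.

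**End imbalance at 40.** With fixed blocks of 6 the last block stops after four places, so the worst split there is 3:1, which gives 21 against 19. With blocks up to 8 it can be 4:0, which gives 22 against 18.

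**The case against.** Several stronger readings are tempting, and the documents do not support them.

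- *The pharmacist's selection is not random.* The text does not say how the seven blocks are chosen. A blind draw of sealed envelopes would be random. All that can be said is that random selection is not described.
- *Ten possible blocks is an error, because there are 20.* This holds only under 1:1 and only if ten means distinct orders. It can equally mean ten prepared envelopes, and then nothing is wrong with the number.
- *Opening an envelope shows the recruiters six assignments.* The pharmacist is the only envelope handler named, and has no stated part in consent, ABPM or scheduling. Single-assignment envelopes grouped by block are not excluded.
- *The trial is declared open-label.* It is not. That the team knows the arm is inferred from Section 6.3, though the inference is hard to avoid.

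It is also fair to say that 23% is an upper bound, since it needs a team that follows every assignment and block boundary. Entry rests largely on measured criteria: three of the last four clinic readings and a repeat ABPM. Candidates come from an existing cohort, and consent precedes screening. This leaves less room to choose who enters, though timing could still be influenced.

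The trial is also mainly about feasibility: "An endpoint for this feasibility trial is to determine the effect size needed to appropriately power a definitive trial of losartan". Acceptance, retention, adherence and pooled change from baseline depend little on which arm a person receives. That narrows the exposure to the between-arm comparisons but does not remove it, because Sections 9.1 and 9.2 do compare the arms and carry the result forward. No size of bias can be derived from the documents.

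**Conclusion.** The point stands as a cheap improvement that should be made. One fixed, published block size combined with visible arms makes 1.5 of 6 assignments per full block (25%), or 9.1 of 40 (about 23%), certain before entry. This rests on two assumptions: 1:1 allocation, and a team that tracks earlier assignments. The five-in-six figure applies only if an opened envelope exposes its whole block to those enrolling.

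What is at risk is the between-arm t-test and the comparison of safety by arm. A reader might go further and infer that the allocation is non-random or that assignments would in fact be steered; the text shows neither. It shows a procedure that permits foreknowledge and does not say how each assignment is concealed until entry.

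**What to change.** Rewrite Section 6.2 to specify:

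1. A 1:1 ratio, stated explicitly.
2. A computer-generated sequence drawn from all balanced orders, prepared by someone outside enrolment. This replaces the selection of seven blocks from ten.
3. Block sizes varied at random, for example 4, 6 and 8, held in a separate document and not disclosed to the enrolling team.
4. One sequentially numbered opaque envelope per participant, opened by the pharmacist only after eligibility and consent are recorded.

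Item 3 cuts certain assignments from about 23% to about 2-3%, but best-guess success stays near 68%. Item 4 closes the whole-block route and fixes each entry before its assignment is seen.

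The cost is a short rewrite and a new list. The largest possible end imbalance at 40 rises slightly, from 21 against 19 to 22 against 18, which matters little for the planned comparison.
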